## 6.15. Protocol Violations

Listings of patients with significant protocol violations will be provided for the Randomized population. The following list of significant protocol violations will be determined from the clinical database and from the clinical/medical group:

- Informed consent violation detected as a missing date of informed consent.
- Did not have an assessment of either the ADAS-Cog or ADL at any of the visits at which the scales were scheduled to be assessed.
- Incomplete infusions (any infusion at which less than 75%, approximately 190 mL, of the infusion solution is given).

The following list of significant protocol violations will be determined by clinical/medical group:

- Protocol violations of inclusion/exclusion criteria.

- Had a study dosing algorithm violation (such as if patients randomized to treatment A were given treatment B or patients randomized to treatment A never received the assigned study drug.)
- Unqualified raters for the ADAS-Cog or ADL.

Other protocol violations reported through the monitoring process will be reviewed by the study team and if judged to be significant, will be added to the final reported listing.

## **6.16. Interim Analyses and Data Monitoring**

An external DMC is authorized to evaluate results from unblinded interim analyses for the assessment of safety, to recommend any modifications to the study (such as stopping the study or dropping an arm), and inform future development. The DMC will have the responsibility to review accumulating unblinded study data and make recommendations to protect the safety of patients. Each member of the DMC is a recognized expert in the fields of Alzheimer's Disease, geriatric neurology, geriatric psychiatry, or biostatistics. All members will be external to the Sponsor. The approved DMC charter enumerates the roles of the DMC members, the frequency with which it meets, and the structure of their meetings. Study sites will receive information about interim results ONLY if relevant for the safety of their patients.

### **6.16.1. Interim Analysis 1**

The objective of the first interim analysis (IA1) is to assess the viability of continuing with at least 1 dose of LY3303560 with regard to safety. An unblinded DMC review for safety will be conducted once approximately 30 patients have completed 3 months of exposure to study treatment (i.e., after completing 4 weeks following the third dose of study treatment). No patients beyond this initial group of approximately 30 patients will be dosed until the DMC review has been completed and the recommendation is to continue the study. This initial group will continue treatment during the assessment period. No statistical adjustments will be made to account for this interim since it is a safety only interim and there is no possibility of stopping for efficacy.

The following analyses will be included in IA1:

- Summary of Patient Disposition
- Summary of Patient Compliance
- Summary of Patient Demographics
- Summary of Patient Baseline Severity
- Summary of Patient Exposure
- Summary of Concomitant Medications
- Summary of Concomitant AChEI/Memantine Medications
- Summaries of Adverse Events (SAEs, DCAE's, TEAE's)

- Listing of Adverse Events
- Summaries of Laboratories (Categorical and Mean Change from Baseline)
- Listing of Laboratories
- Summaries of Vital Signs and Weight (Categorical and Mean Change from Baseline)
- Listing of Vitals Signs and Weight
- Summaries of ECGs (Categorical and Mean Change from Baseline)
- Listing of ECGs
- Summary of Safety MRIs
- Listing of MRIs
- Summary of C-SSRS
- Listing of C-SSRS

#### **6.16.2. Safety Summaries for Interim Analysis 2**

The efficacy analyses used in Interim Analysis 2 (IA2) will be detailed in the Interim Efficacy SAP. In addition to the listings and summaries reviewed at IA1, the following analyses will be included in Interim Analysis 2 (IA2):

- Listing of patients missing site assessments and infusions because of COVID-19
- Listing of patients discontinuing the study because of COVID-19
- Dot plot of visits (x-axis) by patient (y-axis) with color denoting missed infusions
- Summary of ADA
- ANCOVA of change in whole brain volume from vMRI

#### **6.16.3. Interim Analysis 3**

A third unblinded DMC review will be conducted for safety when approximately 100% of patients, have completed 18 months of exposure to study treatment (that is, 4 weeks after the 18th dose at Visit 21 [Week 76]). The following safety analyses will be included:

- Summary of Patient Disposition
- Summary of Patient Demographics
- Summary of Patient Exposure
- Summary of Concomitant Medications
- Summaries of Adverse Events (SAEs, DCAE's, TEAE's)
- Listing of Serious Adverse Events

- Summaries of Laboratories (Categorical and Mean Change from Baseline)
- Listing of Abnormal Laboratories
- Summaries of Vital Signs and Weight (Categorical and Mean Change from Baseline)
- Summaries of ECGs (Categorical and Mean Change from Baseline)
- Summary of Safety MRIs
- Listing of MRIs
- Summary of C-SSRS
- Listing of C-SSRS
- Summary of ADA
- ANCOVA of change in whole brain volume from vMRI

## 6.17. Planned Exploratory Analyses

### 6.17.1. *Exploratory Efficacy Analyses*

#### 6.17.1.1. MMRM Analyses

The additional clinical and outcome measurements listed below will be analyzed separately using an MMRM analysis. The change from baseline at each scheduled postbaseline visit will be the dependent variable. The model for the fixed effects will include the following terms (same as primary efficacy analysis): baseline score, pooled site, treatment, visit, treatment-by-visit interaction, baseline-by-visit interaction, concomitant AChEI and/or memantine use at baseline (yes/no), and age at baseline. The null hypothesis is that the differences in least-squares means between the LY3303560 dose groups versus placebo at Week 104 equal zero. The outcomes that will be analyzed are:

- Change from baseline in CogState Brief Battery (CBB)
- Change from baseline in Digital Clock Drawing Test (DCTClock)

#### 6.17.1.2. Ordinal Regression Analyses

Treatment differences in level of dependence derived from the ADL scale will be assessed using logistic ordinal regression analysis. The logistic ordinal regression model will include independent variables for treatment and concomitant AChEI and/or memantine use at baseline (yes/no). The null hypothesis is that the contrast of LY3303560 groups versus placebo equals zero.

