### 4.3. Exploratory Objectives

The exploratory objectives described in the protocol for study LMDC are in the following table:

Exploratory Objectives	Exploratory Endpoints
To assess the effect of LY3303560 versus placebo on clinical progression in patients with early symptomatic AD.	Change in dependence level derived from ADCS-ADL scale scores from baseline to 104 weeks.
To assess the effect of LY3303560 versus placebo on clinical progression in patients with early symptomatic AD.	Change in cognition from baseline to 104 weeks as measured by the change in: 
 
• CogState Brief Battery (CBB)
 

To assess peripheral PK and presence of anti-LY3303560 antibodies over 104 weeks.	
 
• Maximum serum concentration of LY3303560 at steady state (<math>C_{max,ss}</math>).
 
• Anti-drug antibodies (ADA) against LY3303560 including treatment-emergent ADA and neutralizing antibodies.
 

To assess the effect of LY3303560 versus placebo on clinical progression as measured by Digital Clock Drawing test (DCTClock) in patients with early symptomatic AD.	Change in DCTClock results from baseline through 104 weeks.
To assess the initial effect of LY3303560 versus placebo on plasma total tau and phospho181tau concentrations in patients with early symptomatic AD.	Change from baseline to steady state (16 weeks) in plasma tau and phospho181tau levels.
To assess the steady state effects of LY3303560 versus placebo on plasma tau and phospho181tau concentrations in patients with early symptomatic AD.	Change in plasma tau and phospho181tau concentrations at steady state through 104 weeks.
To assess the utility of DCTClock and plasma phospho181tau in screening phase efficiency for trials of patients with early symptomatic AD.	Associations of DCTClock and plasma phospho181tau with MMSE, CBB, screen failure categories, and baseline data from enrolled subjects.

Additional exploratory objectives not included in the protocol are described in the following table:

To assess the initial effect of LY3303560 versus placebo on plasma ptau217 and Neurofilament light chain (NfL) concentrations in patients with early symptomatic AD.	Change from baseline to steady state (16 weeks) in plasma ptau217 and NfL.
To assess the steady state effects of LY3303560 versus placebo on ptau217 and NfL concentrations in patients with early symptomatic AD.	Change in ptau217 and NfL at steady state through 104 weeks.

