## 6.2. Adjustments for Covariates

The repeated measures models will include the fixed, categorical effects of baseline score, pooled site, treatment, visit, treatment-by-visit interaction, baseline-by-visit interaction, concomitant AChEI and/or memantine use at baseline (yes/no), and age at baseline.

When an analysis of covariance (ANCOVA) model is used to analyze a continuous efficacy variable, the model will contain the main effects of treatment and appropriate baseline value included as a covariate. When an ANCOVA model is used to analyze a continuous safety variable, the model will contain the main effects of treatment, age, and appropriate baseline value included as a covariate.

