## 6.3. Handling of Dropouts or Missing Data

### 6.3.1. *Handling Missing Data from Patient Dropouts*

A likelihood-based mixed effects model for repeated measures will be used to handle missing data. The model parameters are simultaneously estimated using restricted likelihood estimation incorporating all of the observed data. Estimates have been shown to be unbiased when the missing data are missing at random and when there is ignorable non-random missing data.

Repeated measures and disease progression model analyses will only use data from visits where the data was scheduled to be collected (Andersen and Millen 2013). When patients discontinue from the study early, there may be efficacy or safety data measurements at visits where the variables were not scheduled to be collected. This data will be used in all other analyses.

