## 6.8. Patient Characteristics

Baseline characteristics will be summarized for the randomized population by treatment group and overall. Summaries will include descriptive statistics for continuous and categorical measures. Fisher's exact test or Pearson's chi-square test will be used for treatment-group comparisons of categorical data. For continuous data, analysis of variance (ANOVA), with independent factors for treatment, will be used. Patient characteristics to be presented include:

- age
- gender

- race
- ethnicity
- height
- body weight
- body mass index (weight (kg) / [height (m)])
- tobacco use
- alcohol use
- years of education
- work status
- time since onset of first AD symptoms
- tau PET burden (various measures)
- time since diagnosis
- APOE4 carrier status (carrier [ $\epsilon 2/\epsilon 4$ ,  $\epsilon 3/\epsilon 4$ ,  $\epsilon 4/\epsilon 4$ ], noncarrier [ $\epsilon 3/\epsilon 3$ ,  $\epsilon 2/\epsilon 2$ ,  $\epsilon 3/\epsilon 2$ ])
- APOE4 genotype ( $\epsilon 2/\epsilon 4$ ,  $\epsilon 3/\epsilon 4$ ,  $\epsilon 4/\epsilon 4$ , no  $\epsilon 4$ )
- having 1 or more first degree relatives with AD
- AChEI and/or memantine use at baseline

Baseline severity of impairment as measured by ADAS-Cog13, ADCS-ADL total score and instrumental (ADCS-iADL) and basic subscores (ADCS-bADL), CDR Sum of Boxes, MMSE, Cogstate Brief Battery (CBB), and Digital Clock Drawing Test (DCTClock). Baseline characteristics and baseline severity will also be listed.

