#### **6.11.4. Other Secondary Efficacy Analyses**

The additional clinical and outcome measurements listed below will be analyzed separately using an MMRM analysis. The change from baseline at each scheduled postbaseline visit will be the dependent variable. The model for the fixed effects will include the following terms (same as primary efficacy analysis): baseline score, pooled site, treatment, visit, treatment-by-visit interaction, baseline-by-visit interaction, concomitant AChEI and/or memantine use at baseline (yes/no), and age at baseline. The null hypothesis is that the differences in least-squares means between the LY3303560 dose groups versus placebo at Week 104 equal zero. The outcomes that will be analyzed are:

- Change from baseline as obtained from the ADAS-Cog13
- Change from baseline in ADCS-ADL total score
- Change from baseline in ADCS-iADL score
- Change from baseline in ADCS-bADL score
- Change from baseline in CDR-SB
- Change from baseline in MMSE

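### The dependence-level endpoint is a change to Week 104, but its ordinal regression models level, names no visit and omits baseline level: a valid test that can lose power

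*SAP*

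**What the plan says.** The endpoint is in SAP Section 4.3: "Change in dependence level derived from ADCS-ADL scale scores from baseline to 104 weeks".

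The analysis is in Section 6.17.1.2: "Treatment differences in level of dependence derived from the ADL scale will be assessed using logistic ordinal regression analysis". That section names no visit. Of the model terms it says "The logistic ordinal regression model will include independent variables for treatment and concomitant AChEI and/or memantine use at baseline (yes/no", and its hypothesis reads "The null hypothesis is that the contrast of LY3303560 groups versus placebo equals zero".

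Four other places bear on the point:
- Section 6.2 sets the covariates for repeated-measures models, with baseline score among them. For an ANCOVA of a continuous efficacy variable it says "the model will contain the main effects of treatment and appropriate baseline value included as a covariate". It sets no rule for ordinal regression.
- Section 6.17.1.1, immediately before the ordinal regression, lists both baseline score and its interaction with visit.
- Section 6.8 includes in baseline severity the "ADCS-ADL total score and instrumental (ADCS-iADL) and basic subscores (ADCS-bADL" scores, so the source of a baseline dependence level is already collected.
- Section 6.11.4 has a baseline-adjusted MMRM for "Change from baseline in ADCS-ADL total score".

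**The concern.** Read side by side, Sections 4.3 and 6.17.1.2 do not describe the same quantity. The first is a movement from baseline to a fixed week; the second is a level at an unnamed time. Taken literally, Section 6.17.1.2 uses baseline neither in the response nor as a covariate. The SAP's listed change-from-baseline MMRM, slope and ANCOVA treatment comparisons (for example Sections 6.11.3.1, 6.11.3.6, 6.11.3.7, 6.11.4 and 6.12.1 to 6.12.4) all carry baseline, and no reason is given for the difference here.

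Two things are at stake. The choice between level and change is left open until the data are analysed. And power may be lost on the only analysis that this endpoint has.

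**Working it through.** **No figure to reproduce.** The SAP's only stated power (Section 5.2) is for the primary disease progression model, so the size of this point has to come from simulation under assumptions.

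**Inputs from the SAP.** Two-sided alpha is 0.05 (Section 6.1) and allocation is 1:1:1 (Section 5.3). Section 5.2 gives 360 enrolled and 30% dropout: 360/3 = 120 per arm, and 120 × 0.7 = 84.

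**Assumptions not in the SAP.** Treatment shifts latent dependence by 0.35 SD. The latent correlation between baseline and Week 104 is 0.3, 0.5 or 0.7. There are 4 baseline and 5 outcome levels, with three sets of shares (%):
- A: baseline 35/35/20/10, outcome 15/25/30/20/10
- B: baseline 60/30/8/2 (top two merged as covariate), outcome 30/30/25/10/5
- C: even shares

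**Model.** One dose against placebo, logit P(Y ≤ k) = a_k − (b₁·treatment + b₂·AChEI/memantine use), fitted without and with categorical baseline level. The test is Wald: reject if |b₁/SE| > 1.96. There were 4,000 datasets per cell.

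**Power (%) without → with baseline level, 84 per arm**

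| Response | Shares | corr. 0.3 | corr. 0.5 | corr. 0.7 |
|---|---|---|---|---|
| Week 104 level | A | 57.9 → 61.1 | 56.6 → 66.3 | 57.2 → 79.2 |
| | B | 56.2 → 58.5 | 54.5 → 61.7 | 54.4 → 71.8 |
| | C | 57.1 → 60.3 | 55.5 → 65.3 | 55.8 → 77.6 |
| Change | A | 49.6 → 62.9 | 58.7 → 67.1 | 76.3 → 79.0 |
| | B | 52.2 → 60.2 | 58.2 → 62.0 | 71.8 → 72.5 |
| | C | 50.4 → 63.2 | 59.5 → 66.8 | 75.6 → 77.8 |

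The smallest level gain is 58.5 − 56.2 = 2.3 points and the largest is 79.2 − 57.2 = 22.0. For change the range is 72.5 − 71.8 = 0.7 to 62.9 − 49.6 = 13.3. The paired Monte Carlo SE of a gain is 0.3 to 0.8 points. The two responses run in opposite directions: the gain rises with correlation for level and falls for change.

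**Validity.** Simulated type I error without baseline was 4.8 to 6.0% (level) and 4.5 to 5.4% (change). With baseline it was 5.1 to 6.2% and 5.3 to 7.2%. Part of the raw gain is therefore inflated size. With critical values reset to give an empirical 5%, the gains at correlation 0.3, 0.5 and 0.7 are:
- level: 1 to 2, 6 to 10 and 15 to 21 points
- change: 5 to 10, 2 to 5 and 0 to 1 points

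**Where the gain comes from.** For level, shares A, correlation 0.7, the log odds ratio moves from −0.61 (SE 0.281) to −0.82 (SE 0.297). The ratio goes from 0.61/0.281 = 2.17 to 0.82/0.297 = 2.76. The standard error rises slightly; the estimate moves further from zero.

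**Other sample sizes, one distribution (2,000 datasets).** Section 6.3.1 says of early-discontinuation data "This data will be used in all other analyses", which takes in the ordinal regression, so more than 84 per arm may be evaluable. At 120 per arm the gains are 2, 10 and 19 points (level) and 13, 7 and 1 (change). The SAP title page gives about 225 patients: 225/3 × 0.7 = 52.5. At 52 per arm the gains are 3, 8 and 19 (level) and 11, 6 and 3 (change).

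**Different level structure.** With 6 levels, baseline as one linear term and 60% assumed on AChEI/memantine, at 84 per arm:
- level: 57 → 60, 56 → 66 and 57 → 79
- change: 48 → 61, 59 → 67 and 76 → 79

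Beyond the main range, at correlation 0.85, level gives 55 → 90 and change 90 → 90.

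**Clustered baseline.** With assumed baseline shares 85/13/2 (top two merged) and outcome shares 45/30/15/7/3 (1,000 datasets):
- level: 52.8 → 55.3, 49.6 → 54.8 and 50.1 → 61.0
- change: 46.6 → 49.1, 55.2 → 54.9 and 62.4 → 62.8

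The change gain is then about 0 to 2.5 points. One power estimate here has a Monte Carlo SE near √(0.5 × 0.5/1000) = 1.6 points, so the 0.3-point fall is noise.

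**The case against.** The strongest reply is that nothing here is an error. Section 6.2 does not reach ordinal regression, the test keeps its size, and a sparse model for one exploratory comparison is a legitimate choice. It stands that no SAP rule is broken. It does not remove the mismatch between Sections 4.3 and 6.17.1.2, and adjusting for an already collected baseline value is a concrete improvement rather than a matter of taste.

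A second reply is that Section 4.3 supplies both the change and the week, so the response is change and little is lost. This largely stands for power: the size-adjusted gain is then 0 to 10 points and may be near nil. A reader might carry the 22-point figure over to the stated endpoint, but that figure belongs to the Week 104 level reading only.

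A third reply is that adjustment is not free. That also stands:
- The adjusted odds ratio is conditional on baseline level, so it is a different quantity from the unadjusted one.
- The adjusted Wald test can run slightly above 5%.
- With shares B left unmerged, the adjusted change model gave no estimate in 266 of 4,000 datasets at correlation 0.3. Merging removed this.

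**Conclusion.** The mismatch and the omission are both in the text. The consequence is a valid test that can be less efficient than it need be. At 84 per arm, an effect of 0.35 latent SD and correlations of 0.3 to 0.7, adding baseline level is worth about 2 to 22 points of power for Week 104 level (size-adjusted 1 to 21). For change it is worth about 0 to 10 points size-adjusted, close to nil at correlation 0.7 or with clustered baseline levels. All of these rest on assumed level shares, correlation and effect.

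A reader might infer that leaving out baseline biases the comparison or makes the test invalid. The documents do not support that: treatment is randomised, and simulated type I error without baseline stays near 5%. This assumes that dropout does not differ by arm in a way linked to baseline. Nor does the SAP support reading Section 6.2 as a rule that was breached.

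The point is low in importance. The analysis is exploratory and outside the gated scheme of Section 6.11.2, and ADCS-ADL already has a baseline-adjusted analysis.

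**What to change.** In Section 6.17.1.2:
- State that the response is dependence level at Week 104.
- Add baseline dependence level as a categorical covariate, with a pre-stated rule for merging sparse levels.
- Say that this model is how the change endpoint of Section 4.3 is analysed, so that the two sections agree.
- Note that the odds ratio is conditional on baseline level. A likelihood-ratio test may be used in place of the Wald test.

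Going from unadjusted change to baseline-adjusted Week 104 level takes power from 49.6 to 61.1, 58.7 to 66.3 and 76.3 to 79.2% with shares A (correlation 0.3, 0.5 and 0.7). With shares B at 0.7 it stays at 71.8%. The cost is a few lines of SAP text and one model term, with no new data.

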## 6.17.2. *Exploratory Bioanalytical and PK/PD Analyses*

### 6.17.2.1. Analysis of Neurofilament Light Chain (NfL)

To evaluate the change from baseline in Neurofilament Light chain (NfL), an MMRM analysis will be used to compare change from baseline at 104 weeks in the Evaluable Efficacy dataset. The model will include the fixed, categorical effects of treatment, visit, and treatment-by-visit interaction, as well as continuous effects of baseline log(NfL) and age at baseline. The NfL values will be log transformed prior to calculating the changes from baseline. Visit will be considered a categorical variable with values equal to the visit numbers at NfL is assessed. The null hypothesis is that the difference in LSM between the LY3303560 dose groups and placebo equals zero.

Change from baseline and annualized change from baseline analyses will be conducted on NfL. The annualized change will be compared between the treatment groups with an ANCOVA on the full efficacy dataset. The ANCOVA model will include the fixed effect of treatment as well as continuous effects of baseline NfL value and age at baseline. The null hypothesis is that the difference in LSM between the LY3303560 dose groups and placebo equal zero.

To assess the relationship of biomarker with cognition and function with treatment, Spearman's rank correlation coefficient will be obtained on change from baseline to Week 104 for the NfL and with change from baseline to Week 104 for iADRS, ADAS-Cog13, ADCS-ADL, MMSE, and CDR-SB. Correlation analyses will be conducted using only patients who have the clinical outcome and SUVr result at Week 104 and include patients from all 3 dose groups.

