# 1. Statistical Analysis Plan: I8G-MC-LMDC: Assessment of Safety, Tolerability, and Efficacy of LY3303560 in Early Symptomatic Alzheimer's Disease

## Confidential Information

The information contained in this document is confidential and the information contained within it may not be reproduced or otherwise disseminated without the approval of Eli Lilly and Company or its subsidiaries.

**Note to Regulatory Authorities:** This document may contain protected personal data and/or commercially confidential information exempt from public disclosure. Eli Lilly and Company requests consultation regarding release/redaction prior to any public release. In the United States, this document is subject to Freedom of Information Act (FOIA) Exemption 4 and may not be reproduced or otherwise disseminated without the written approval of Eli Lilly and Company or its subsidiaries.

LY3303560

Alzheimer's disease

Multicenter, randomized double-blind, placebo-controlled, Phase 2 study comparing up to 5600 mg of LY3303560 with placebo over 104 weeks in approximately 225 patients with early symptomatic AD.

Eli Lilly and Company  
Indianapolis, Indiana USA 46285  
Protocol I8G-MC-LMDC  
Phase 2

SAP electronically signed and approved by Lilly on date provided below:

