### 5.2. Determination of Sample Size

Based on the Disease Progression Model (DPM), 360 enrolled patients, a 30% dropout rate, and a 3-month delay of treatment effect onset, this sample size will provide more than 95% power to

demonstrate that at least one of the active treatment arms has slowed cognitive/functional decline. This claim of slowing cognitive/functional decline is based on showing that at least one of the active treatment arms has a  $\geq 0.6$  posterior probability of slowing of iADRS progression over placebo by at least 4 points (that is, 25% slowing relative to placebo, based on a mean change from baseline in the placebo group of 16 points and mean change from baseline on at least one of the active treatment arms of at most 12 points) after 104 weeks (approximately 24 months) on study treatment. This power calculation comes from simulations using a placebo decline of 19.56 points and 33% slowing on 1400 mg LY3303560 and 50% slowing on 5600 mg LY3303560 relative to placebo at 104 weeks. The variance-covariance matrix in the simulations had a variance at Week 104 of 436.85 (equal to a standard deviation of 20.9). If both active treatment arms are placebo-like with no efficacy, the probability of passing the efficacy criterion specified above (that is, false positive) is approximately 2.5%. To test the hypothesis of a disease progression benefit, we calculate the posterior probability of superiority in cognitive/functional slowing, and if it is above a pre-specified threshold (which controls the experiment-wise type I error at approximately 2.5%), then a claim of cognitive slowing will be made. The simulation for the power calculation and sample size determination was carried out in FACTS Version 5.5.

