## **6.12. Bioanalytical and Pharmacokinetic/Pharmacodynamic Methods**

### **6.12.1. Analysis of flortaucipir PET**

To evaluate the change from baseline in tau imaging parameters, an MMRM analysis will be used to compare change from baseline in SUVR at 104 weeks in the Evaluable Efficacy dataset. The model will include the fixed, categorical effects of treatment, visit, and treatment-by-visit interaction, as well as continuous effects of baseline SUVR and age at baseline. Visit will be considered a categorical variable with values equal to the visit numbers at which tau imaging is assessed. The null hypothesis is that the difference in LSM between the LY3303560 dose groups and placebo equals zero.

To assess the relationship of biomarker with cognition and function with treatment, Spearman's rank correlation coefficient will be obtained on change from baseline to Week 104 for the composite summary standard uptake value ratio (SUVR) normalized to bimodal white matter and with change from baseline to Week 104 for iADRS, ADAS-Cog13, ADCS-ADL, MMSE, and CDR-SB. Correlation analyses will be conducted using only patients who have the clinical outcome and SUVR result at Week 104 and include patients from all 3 dose groups.

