### **6.12.4. Analysis of vMRI**

Analyses of the following volumetric MRI (vMRI) parameters will be conducted (right + left for all but whole brain volume and ventricular volume):

- Hippocampal volume (cm^3)
- Entorhinal cortex (cm^3)
- Inferior parietal lobe (cm^3)
- Isthmus cingulate (cm^3)
- Lateral parietal lobe (cm^3)
- Medial temporal lobe (cm^3)
- Precuneus (cm^3)
- Prefrontal lobe (cm^3)
- Superior temporal lobe (cm^3)
- Cortical (cm^3)
- Whole temporal lobe (cm^3)
- Atrophy of total whole brain volume (cm^3)
- Enlargement of Ventricular volume (cm^3)
- White Matter (cm^3)
- White Matter Hypo Intensities (cm^3)

All of the above volumes are corrected for intracranial volume. To evaluate the changes in vMRI data after treatment, an MMRM analysis will be used to compare change from baseline to 104 weeks in the Evaluable Efficacy dataset. The change from baseline to the endpoint visit will be the dependent variable. The model will include the fixed, categorical effects of treatment, visit, and treatment-by-visit interaction, as well as continuous effects of baseline vMRI, baseline intracranial volume (ICV) and age. The null hypothesis is that the difference in LSM between the

LY3303560 active dose groups and placebo equal zero. A similar analysis will be performed for completers.

To assess the relationship of vMRI with cognition and function with treatment, Spearman's rank correlation coefficient will be obtained on change from baseline to Week 104 for vMRI parameters with change from baseline to Week 104 for iADRS, ADAS-Cog13, ADCS-ADL, MMSE, and CDR-SB; this will be performed using all patients who have the clinical outcome and vMRI result at Week 104; adjusted for age, baseline intracranial volume (ICV), and sex; and include patients from both treatment groups.

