### 6.17.2.2. Analysis of Plasma Tau

To evaluate the change in plasma tau analytes (including assayed plasma total tau and p-tau) after treatment, an MMRM will be used to compare change from baseline to 104 weeks. The plasma tau values will be log transformed prior to calculating the changes from baseline. This analysis will be run separately for each plasma tau parameter using the Evaluable Efficacy dataset. The model will include the fixed, categorical effects of treatment, visit, and treatment-by-visit interaction, as well as the continuous effect of baseline log(plasma tau). Visit will be considered a categorical variable with values equal to the visit numbers at which plasma tau is assessed. The null hypothesis is that the difference in LSM between the LY3303560 dose groups and placebo equal zero. A similar analysis will be performed for completers.

To assess the relationship of plasma tau with cognition and function with treatment, Spearman's rank correlation coefficient will be obtained on change in plasma tau from baseline to Week 104 and with change from baseline to Week 104 for iADRS, ADAS-Cog13, ADCS-ADL, MMSE, and CDR-SB. Correlation analyses will be conducted using only patients who have the clinical outcome and plasma tau result at Week 104.

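### The NfL correlation in SAP 6.17.2.1 requires a Week 104 tau PET result, not an NfL result, and as worded could exclude patients who have the data it needs

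*SAP*

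**What the plan says.** SAP Section 6.17.2.1 sets up the correlation in these terms: "Spearman's rank correlation coefficient will be obtained on change from baseline to Week 104 for the NfL and with change from baseline to Week 104". The clinical scales concerned are iADRS, ADAS-Cog13, ADCS-ADL, MMSE and CDR-SB. The sentence that follows sets the inclusion rule: the analysis is done "using only patients who have the clinical outcome and SUV r result at Week 104", pooling all three arms.

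The SAP plans three other correlations of a biomarker with the clinical scales, each with its own inclusion rule:

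- Flortaucipir PET (6.12.1): "using only patients who have the clinical outcome and SUVR result at Week 104 and include patients from all 3 dose groups".
- Volumetric MRI (6.12.4): "using all patients who have the clinical outcome and vMRI result at Week 104".
- Plasma tau (6.17.2.2): "using only patients who have the clinical outcome and plasma tau result at Week 104".

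Section 6.12.1 also makes clear what SUVR is in this document. It is the tau imaging outcome, for which "an MMRM analysis will be used to compare change from baseline in SUVR at 104 weeks in the Evaluable Efficacy dataset".

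**The concern.** A correlation of NfL change with clinical change needs two things from each patient: an NfL change and a clinical change. The rule in 6.17.2.1 names the clinical outcome, leaves out NfL, and adds a PET measurement that plays no part in the calculation.

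This sentence decides who enters the analysis, so it is not background text. A programmer who follows it would exclude any patient with NfL and clinical data at Week 104 but no PET result. The NfL correlation could then rest on a different set of patients from the plasma tau correlation in the next subsection, for no stated reason, which weakens a side-by-side reading of the two blood markers. A programmer who instead assumes that NfL was meant would depart from the written plan without a record of it.

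**Working it through.** **Step 1. Compare the four inclusion rules.**

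| SAP section | Biomarker correlated | Week 104 result required besides the clinical outcome | Match? |
|---|---|---|---|
| 6.12.1 | SUVR | SUVR | yes |
| 6.12.4 | vMRI | vMRI | yes |
| 6.17.2.2 | plasma tau | plasma tau | yes |
| 6.17.2.1 | NfL | SUVr | **no** |

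Three of the four rules require the biomarker being correlated; only the NfL rule requires a different one. Its sentence matches the one in 6.12.1 almost word for word, including the closing clause about all three dose groups, which the plasma tau rule lacks. Carry-over from 6.12.1 is therefore the likeliest explanation.

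**Step 2. Look for a reason for a PET condition.** Section 6.17.2.1 gives none, and no other section of the SAP does. If a common PET subset had been wanted so that biomarkers could be compared in the same patients, the vMRI and plasma tau rules would be expected to carry the condition too. They do not.

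**Step 3. Size of the effect.** The SAP states no sample size, precision or alpha for this correlation, so there is no figure of its own to reproduce. It also gives no rate of missing PET at Week 104. Let x be the fraction of patients with NfL and clinical data at Week 104 who have no SUVr result. The usable number falls from n to n(1-x), and the standard error rises by about 1/sqrt(1-x). Every non-zero x below is an assumption:

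| x (assumed) | 1/sqrt(1-x) |
|---|---|
| 0 | 1.00 |
| 0.05 | 1.03 |
| 0.10 | 1.05 |
| 0.20 | 1.12 |
| 0.30 | 1.20 |

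**Step 4. Illustration in patient numbers.** Section 5.2 plans on "360 enrolled patients, a 30% dropout rate, and a 3-month delay of treatment effect onset". The SAP's opening description instead has treatment compared "over 104 weeks in approximately 225 patients with early symptomatic AD". Both totals are used here, with the same 30% dropout and the further assumption that everyone still in the study at Week 104 has NfL and clinical data. The approximate 95% half-width on the Fisher z scale is 1.96/sqrt(n-3).

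- From 360: 360 × 0.70 = 252, half-width 1.96/sqrt(249) = 0.124.
  - At x = 0.05 about 13 patients are lost, leaving 239: 1.96/sqrt(236) = 0.128.
  - At x = 0.20 about 50 are lost, leaving 202: 1.96/sqrt(199) = 0.139.
- From 225: 225 × 0.70 = 157.5, about 158, half-width 1.96/sqrt(155) = 0.157.
  - At x = 0.05 about 8 are lost, leaving 150: 1.96/sqrt(147) = 0.162.
  - At x = 0.20 about 32 are lost, leaving 126: 1.96/sqrt(123) = 0.177.
- At x = 0, nobody is lost in either case.

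The half-width formula is an approximation for a rank correlation and serves only to show scale.

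**The case against.** The best defence is that this is a drafting slip with a recoverable meaning. The sentence before the rule names the correlated variables correctly, and a Spearman coefficient on NfL change cannot be computed without NfL values, so the missing NfL condition is implied. That stands, and it is why the point is an internal inconsistency to correct, not a dispute over method. It does not dispose of the PET condition, which is an explicit extra restriction that the calculation does not make redundant.

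A second defence is that little depends on the correlation. It sits under the planned exploratory analyses in 6.17, has no hypothesis or decision rule attached, and is outside the multiplicity graph of 6.11.2. The NfL treatment comparisons (the MMRMs in 6.12.2 and 6.17.2.1 and the ANCOVA in 6.17.2.1) are defined on the efficacy dataset without a PET condition. All of this stands.

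A reader might infer three stronger things that the SAP does not support:

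- *That the sponsor chose a PET subset.* Nothing in the text presents it as a choice, and the parallel sections point to carry-over.
- *That patients will in fact be lost.* This requires some patients to have NfL and clinical data at Week 104 but no SUVr result, and the SAP gives no count or rate.
- *That those retained are selected for tolerating a scan.* Tau PET is part of eligibility (5.1), so enrolled patients have already undergone one, and PET through Week 104 serves a secondary objective (4.2). The SAP does not link missing scans to tolerance or show that such selection would bias the correlation.

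**Conclusion.** The inclusion rule in 6.17.2.1 is wrong as written: it requires a measurement that is not in the correlation and does not name the one that is. This conclusion rests on the text alone.

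The consequence is conditional. The rule could exclude patients with usable data, at a cost in precision of about 1/sqrt(1-x), and the cost is nil if no patient with NfL and clinical data lacks a Week 104 PET result. The values of x shown are illustrations, not estimates, because the SAP gives nothing to anchor them. Importance is low: no primary, secondary or gated conclusion changes.

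**What to change.** In SAP Section 6.17.2.1, replace *SUVr result* with *NfL result* in the sentence that sets the patients for the correlation, so that it follows the same pattern as 6.12.4 and 6.17.2.2. If a PET-restricted set is in fact intended, say so and give the reason.

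The cost is a one-word correction. It needs no new data and no change to any other analysis.
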